8.2.5.2.2. Safety Measures

The Patient Rated Inventory of Side Effects (PRISE), CADSS, and Barnes Akathisia Scale (BARS) (including the global severity rating) will be evaluated within and between study treatment groups. Mean changes from baseline for the differences from baseline and after randomization baseline will be evaluated using a paired t-test within each study group and an unpaired t-test for K/N vs. K/L and K/P.

8.2.5.2.3. Other Safety Measures

It is expected that some subjects in both groups (more among those randomized to placebo+lurasidone and placebo) will have recurrence of their depression and, possibly suicidality. Therefore, the investigators plan to effect careful surveillance of all study subjects as follows:

Subjects who receive ketamine will be maintained under continuous professional observation until stabilization is documented or ketamine is deemed not to have achieved stabilization and the treating physician has elected another therapeutic option (which in most cases will be hospitalization with ECT). In general, study subjects will be maintained under direct observation in a mental health center or inpatient setting during the 24 hour stabilization period. At the election of the treating physician in consultation with the patient and family, patients may return home during the 24 hour stabilization period, provided the treating physician has made

arrangements with the patient and family to maintain close professional contact during this period and a responsible adult will be escorting the patient at all times. Participants who cannot ensure a reliable adult transport will not be allowed to enroll in the study. Subjects will be instructed not to drive or operate heavy machinery for at least 24 hours post-administration.

Daily contact with a physician, psychologist, or psychiatric nurse who will assess symptoms and any subject or family/significant other concerns. The contact will be either through a telephone or actual visit. All on-site study visits will include a meeting with a study psychiatrist.

The study will employ the use of HIPAA-compliant, electronic video monitoring of medication compliance, with the capability to send an immediate alert for outreach with any missed doses of medication. A non-adherence period of 12 hours (i.e. 2 missed doses will trigger outreach by study personnel).

In case of loss of phone contact or repeated non-adherence to medication, study staff will contact an identified family member/significant other. If study staff determines that hospitalization is urgent, either the family member will take the subject to the emergency room or the staff will contact 911 for an ambulance.

The investigators recognize that although DCS has been used as an anti-infective in millions of individuals without report of significant safety concerns, DCS has thus far been used in 21 subjects at the 1000mg dose in formal studies of psychiatric illness. Therefore, the study medical monitors will surveil for safety issues via frequent safety listings reviews.

The timing and incidence of adverse findings will be compiled following planned surveillance of all study subjects by study medical monitors. The number of such episodes will be evaluated using a Poisson regression model to compare study treatment groups controlling for C-SSRS 24 hours post infusion (1, 2), age (<25, 25-39, ≥40), and gender.

Vital signs will be obtained at every office visit. ECGs will be measured at the Screen Visits, and at Visits 1, 5, and 10. Digital ECGs will be obtained after the subject has been resting in a semi-recumbent position for at least 10 minutes. All digital ECGs will be documented by recording date, time, heart rate, QRS duration, PR interval, RR interval, QT, and QTcF intervals. Mean differences will be calculated using the Fridericia formula (Puddu et al., 1988). Vital signs and ECGs will also be evaluated within and between study treatment groups. If indicated, additional ECG assessments can be made at the discretion of the investigator. The investigator will judge the overall interpretation as normal or abnormal. If abnormal, it will be decided as to whether or not the abnormality is clinically significant or not clinically significant and the reason for the abnormality will be recorded on the eCRF. Abnormal values shall not be recorded as AEs unless deemed clinically significant.

At the Screen visit, and at Visits 1, 5, and 9, subjects will have their blood drawn for chemistry and CBC blood tests. At Screen, and at Visits 5 and 10, subjects will have a physical examination. If these tests or exams are abnormal per established site-specific normal ranges, it will be decided by the site investigator whether or not the abnormality is clinically significant or

not clinically significant and recorded on the eCRF. Abnormal and clinically significant lab values will be reported as AEs if they fulfill any of the SAE criteria or are the reason for discontinuation of treatment with the study drug. Abnormal lab values (clinically significant and clinically non-significant), will be reviewed monthly by the medical monitor for trends. Should any abnormal lab values exceed rates described in the IB, the FDA and SPONSOR will be notified within regulatory timelines. McNemar paired comparison tests will be performed within study treatment groups for the abnormal percents while two-sided Fisher Exact tests will be performed between treatment groups.

8.2.6 Study Instruments

Study instruments will be administered in accordance to the schedule in Table 3.

8.2.6.1 Efficacy Measures

Bipolar Inventory of Symptom Scale (BISS) (Bowden et al., 2007): The BISS is a 44-item clinician-rated scale (22 items for the depression subscale and 22 items for the mania scale), in which each item is rated on a 0-4 severity scale which is which operationally defines each item, confining the assessment to only one behavioral construct. Items are grouped into 10 established symptom clusters, based on prior studies of phenomenology and reports of symptom clusters and principal components in ratings of BD. The timeframe for the BISS is the past 7 days. The BISS scale has been found to have high internal consistency (Chronbach's alpha=0.93 for the Total Scale, 0.92 for the depression subscale, and 0.90 for the mania subscale) and inter-rater reliability (ICC=0.96 for total scale, 0.98 for depression subscale, and 0.95 for mania subscale) (Gonzalez, et al, 2008). Regarding discriminant validity, the BISS total score was able to significantly distinguish between patients in a depressed, manic or mixed episode from subsyndromal patients, recovered patients, and healthy controls (Gonzalez et al, 2008). Convergent validity was demonstrated by strong Pearson correlations (i.e., $r=.64$ to $.94$) between the BISS total score and the BISS depression subscale and the MADRS, and between the BISS total score and the mania subscale and the YMRS across all patient and control groups described above; divergent validity was demonstrated by smaller and (i.e., $r=-.14$ - 0.30) correlations between the BISS depression subscale and the YMRS scale, and between the BISS mania scale and the MADRS ($r=-.06$ - $.31$).

The Columbia Suicide Severity Rating Scale (C-SSRS) (Posner et al., 2007): The C-SSRS is a low-burden measure of the spectrum of suicidal ideation and behavior that was developed in the National Institute of Mental Health Treatment of Adolescent Suicide Attempters Study to assess severity and track suicidal events through any treatment. It is a clinical interview providing a summary of both ideation and behavior that can be administered during any evaluation or risk assessment to identify the level and type of suicidality present. The C-SSRS can also be used during treatment to monitor for clinical worsening. The C-SSRS will be performed to assess suicidal ideation and behavior. C-CASA is the retrospective counterpart of the more detailed

classification instrument C-SSRS. The C-SSRS tool was first developed for a prospective national study of treatment for adolescent suicide attempts. C-SSRS was developed by reliance on evidence stemming from two decades of research. It contains a 1-to-5 rating scale for suicidal ideation of increasing severity (from a “wish list to die” to an “active thought of killing oneself with plan and intent”), in contrast to C-CASA, which only has one ideation item. (IOM, 2010) The time frame is for both lifetime and the past six months for the Baseline/Screening scale and since the last visit for the Since Last Visit scale.

Brief Psychiatric Rating Scale (BPRS) (Overall & Gorham, 1962): The BPRS is an 18-item clinician rated scale that is used to assess a range of psychotic and affective symptoms, rated from both observation of the subject and the subject’s own report. It has been widely used to measure change in pharmacologic and nonpharmacologic treatment trials and provides a rapid and efficient evaluation of treatment response in clinic drug studies and in clinical settings. Only the 4-item positive symptom subscale BPRS+ (i.e., suspiciousness, hallucinations, unusual thought content, and conceptual disorganization) will be used in this study. It is highly sensitive to change, and excellent inter-rater reliability can be achieved (i.e., ICC>.80) with training and a standard interview procedure. Concurrent validity has been established by $r=.92$ between the positive symptom subscale and the corresponding subscale of the Positive and Negative Syndrome Scale, and sensitivity to change has been demonstrated by significant associations in change between the BPRS total score and the CGI and the HDRS.

Concise Health Risk Tracking – Self Report (CHRT-SR) and Clinician Rating (CHRT-C) scales (Trivedi et al, 2011): This is both a subject self-report assessment of suicidality and related thoughts and behaviors, with a corresponding clinician rated scale. The scales are designed to quickly and easily track suicidality in a manner consistent with the Columbia Classification Algorithm of Suicide Assessment (C-CASA) (Posner et al, 2007). The CHRT-SR is a 16-item self-report suicidal ideation scale and the CHRT-C is a 9-item clinician-rated behavioral module. Items are rated on a fully anchored 5-point Likert scale with responses ranging from 1 (strongly disagree) to 5 (strongly agree). The time frame is the past seven (7) days. The CHRT-SR has good internal consistency (Cronbach's alpha 0.88-0.90), convergent validity with MADRS suicide item ($r=.60$) and QIDS suicide item ($r=0.59$), and divergent validity with the YMRS ($r=.02$). Predictive validity was established by prospective prediction of suicidality-related serious adverse events among 482 patients with bipolar disorder in a multicenter trial (Reilly-Harrington et al, 2016).

Suicidal Ideation and Behavior Questionnaire (SIBQ): The purpose of this instrument is to ensure clinicians properly assess and document suicidal ideation and behavior as well as any study decisions (study exclusion of subject, filing of a serious adverse event) pertaining to suicidality. It will be completed by site investigators during all visits.

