6.2 Methods

[figure not shown]
In Stage 1 eligible subjects will initially receive an infusion of open-label ketamine 0.5mg/Kg. Those who do not respond to ketamine infusion as measured by a $\geq 25\%$ improvement in the MADRS subset on the BISS and a reduction in C-SSRS suicidal ideation to ≤ 3 at 24 hours post infusion will be withdrawn from the study and treated according to standard of care for subjects with suicidal ideation or behaviors.

Subjects who respond successfully to ketamine infusion, as defined above ($\geq 25\%$ improvement in the MADRS subset of the BISS and C-SSRS ≤ 3) at 24 hours post infusion will proceed to Stage 2 and be randomized to either experimental drug NRX-101 (DCS + lurasidone), lurasidone alone, or placebo. Efficacy data will be collected for the subjects responding to ketamine through 6 weeks or until earlier rescue.

Subjects may be terminated from the study and rescued with alternative therapy at any time if, in the opinion of the investigator, subjects have a significant safety risk for clinical deterioration or suicide.

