6.4 Study Population

The study analyses will be conducted in a GCP environment (ICH E6). All analyses will be pre-specified in a Statistical Analysis Plan (SAP) prior to beginning subject enrollment. The study will have prospectively defined study populations including separate evaluability rules for the ketamine treatment (Stage 1) and randomized treatment (Stage 2).

For Stage 1, the Intent-to-Treat (ITT) population will include all subjects who received the ketamine infusion and have the 24-hour post-infusion efficacy assessments. The Per-Protocol Population will include the subset of ITT subjects who were eligible, who had the 24-hour post-infusion efficacy assessments within 18 to 30 hours post the start of the initial infusion, and who had no major protocol violations. The Safety Population will include all subjects treated with ketamine who have any post-baseline safety data.

For Stage 2, the ITT population will include all subjects who received the randomized study treatment and have any post-baseline efficacy assessments. The Per-Protocol population will include the subset of ITT subjects who were eligible, who have any post-baseline efficacy assessments within 1 day of scheduled visits through Day 7 and within 2 days of scheduled visits through Day 42, and who had no major protocol violations. The Safety Population will include all subjects as treated with study treatment who have any post-baseline safety data through Day 70.

The ITT population will be used for the primary analyses. If <5% are to be excluded from the ITT population, then the analysis will not be performed for the PP population.

Every effort will be made to encourage subjects to comply with the procedures and the assessments involved in study. Non-compliance will be tracked. Protocol violations will be reviewed in real time; rules will be set for exclusions from the PP population.

A sufficient number (estimated to be 192 subjects) will be entered into Stage 1 in order to have 124 randomized subjects to complete Stage 2. IRB-approved written informed consent will be obtained from all subjects before any protocol-specified procedures are carried out. The subjects will be drawn from a sample of subjects with BD with suicidal ideation, diagnosed with the use of the MINI 7.0.2 for DSM 5. For entry into the study, all inclusion criteria must be met, and none of the exclusion criteria can be met.

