7.1 Inclusion Criteria

1. Male or female, 18 to 65 years of age, inclusive, at screening.
2. Able to read, understand, and provide written, dated, informed consent prior to screening. Participants will be deemed likely to comply with study protocol and communicate with study personnel about AEs and other clinically important information.
3. Diagnosed with BD according to the criteria defined in the DSM-5. The diagnosis of BD will be made by a site psychiatrist and supported by the MINI 7.0.2. The diagnosis will be confirmed by remote, independent raters via teleconference between the screen visit and the baseline visit.
4. Suicidal ideation or behavior of sufficient severity to meet the requirements for a score of 4 or 5 on the C-SSRS.
5. A score equal to or greater than 20 on the MADRS items of the BISS.
6. In good general health, as ascertained by medical history, physical examination (PE) (including measurement of seated vital signs), clinical laboratory evaluations, and electrocardiogram (ECG).
7. If female, a status of non-childbearing potential or use of an acceptable form of birth control per the following specific criteria:
 - c. Non-childbearing potential (e.g., physiologically incapable of becoming pregnant, i.e., permanently sterilized [status post hysterectomy, bilateral tubal ligation], or is post-menopausal with her last menses at least one year prior to screening); or
 - d. Childbearing potential, and meets the following criteria:
 - iv. Childbearing potential, including women using any form of hormonal birth control, on hormone replacement therapy started prior to 12 months of amenorrhea, using an intrauterine device (IUD), having a monogamous relationship with a partner who has had a vasectomy, or is sexually abstinent.
 - v. Negative urinary pregnancy test at screening, confirmed by a negative urinary pregnancy test at randomization prior to receiving study treatment.
 - vi. Willing and able to continuously use one of the following methods of birth control during the course of the study, defined as those which result in a low failure rate (i.e., less than 1% per year) when used consistently and correctly: implants, injectable or patch hormonal contraception, oral contraceptives, IUD, double-barrier contraception, sexual abstinence. The form of birth control will be documented at screening and baseline.
8. Body mass index between 18-35 kg/m².

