8.1.6 Randomization

Subjects will be assessed in person 24 hours post-infusion for response to ketamine. Those who do not respond will be provided standard of care for ongoing suicidal ideation. Following the documented observance of a therapeutic response to intravenous ketamine as defined by a 25% or greater reduction in the on the MADRS subset of the BISS score and a score of ≤ 3 on the C-SSRS at 24 hours post infusion, subjects will be randomized 2:1:1 to either a fixed dose combination of experimental drug NRX-101 (DCS + lurasidone), or to an identical capsule containing placebo + lurasidone, or to an identical capsule containing placebo. Randomization blocks will be allocated at the site level to ensure that treatment and control groups are balanced per site. An Interactive Web Response System will be used.

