8.1.8 Post Ketamine Infusion Follow-Up

Subjects who are non-responders at 24 hours following the start of the ketamine infusion will be withdrawn from the study and treated according to the site’s standard treatment procedure. Non-response is defined as less than a 25% reduction on the MADRS subset of the BISS score and a score of ≥ 4 on the C-SSRS.

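### The 24-hour ketamine-response gate rests on a scale with a stated 7-day recall, so about six of the seven rated days precede the infusion

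*Combined protocol and SAP*

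**What the plan says.** Section 8.2.6.1 gives the BISS a single recall period: "The timeframe for the BISS is the past 7 days". Section 8.2.6 adds: "Study instruments will be administered in accordance to the schedule in Table 3". Table 3 places the BISS at screening, ketamine dosing, 4 hours, 24 hours and the Stage 2 clinic visits from Day 7. No section gives a different recall for any of these ratings. Table 3 lists no separate MADRS, so the MADRS named in sections 8.2.3, 9.3 and 13.2 can only be the BISS items.

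Section 8.1.6 requires a "25% or greater reduction in the on the MADRS subset of the BISS score", together with a C-SSRS of 3 or less, at 24 hours. Section 6.2 states the same pair, and says that subjects who meet it "at 24 hours post infusion will proceed to Stage 2 and be randomized to either experimental drug NRX-101". Section 8.1.8 gives the other branch: "Subjects who are non-responders at 24 hours following the start of the ketamine infusion will be withdrawn from the study". Section 8.1.8 words non-response as failing both parts. Sections 6.2 and 8.1.6 require both parts for randomisation, so the BISS part is necessary on either wording.

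Other scales have recall suited to their timing. The post-baseline C-SSRS asks about the time since the last visit (section 8.2.6.1), and the CADSS and BARS ask about the present moment (section 8.2.6.2).

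**The concern.** The gate is meant to detect a change that began one day earlier, using a rating that by its stated rule covers a week. A rater who follows section 8.2.6.1 literally is describing mostly the days before the infusion. A rater who scores the patient's current state can record the whole response. Both could be trained and certified, and they could classify the same patient differently.

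Three things depend on this reading:
- which patients make up the enriched, randomised population;
- the 70% response rate that takes 177 Stage 1 completers to 124 randomised (section 13.8.2);
- the 24-hour BISS score where it serves as the Stage 2 baseline for change scores (sections 11 and 13.10.3).

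A responder withdrawn at the gate because of the recall window is lost to Stage 2.

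**Working it through.** **The plan's own figure.** Section 13.8.2 and Table 12: 192 enrolled less 8% gives 192 × 0.92 = 176.6, about 177. Then 177 × 0.70 = 123.9, about 124. The stated figure reproduces.

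**Share of the window before the infusion.** The window is 7 × 24 = 168 hours. Section 6.4 defines the Stage 1 per-protocol set as those "who had the 24-hour post-infusion efficacy assessments within 18 to 30 hours post the start of the initial infusion". The share after the infusion is hours since infusion ÷ 168.

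| Rating at | After infusion | Before infusion |
|---|---|---|
| 18 h | 18/168 = 10.7% | 89.3% |
| 24 h | 24/168 = 14.3% | 85.7% |
| 30 h | 30/168 = 17.9% | 82.1% |

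This step needs no assumption about how raters score.

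**Largest fall that can be recorded.** The documents do not say how an item combines the days in its window, so the following are assumptions.

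- *Equal weight on each day, constant severity before the infusion.* Complete remission lowers the score by the post-infusion share: 14.3% at 24 h, and 10.7% to 17.9% over 18 to 30 h. The 25% mark is first reachable at 0.25 × 168 = 42 h. In points, the inclusion criterion in section 7.1 is "A score equal to or greater than 20 on the MADRS items of the BISS". At a score of 20 the gate needs a fall of 5 points, while one symptom-free day in seven gives 20/7 = 2.9.
- *Worst day in the window.* The recorded change at 24 h is 0%.
- *Weight w on the post-infusion state.* Recorded fall = w × true fall, so the gate needs a true fall of at least 25%/w. A true fall of 50% passes only if w is at least 0.5, and a true fall of 25% passes only if w = 1.

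**Pass rate under partial weighting.** Assume that true falls are normal with 70% of patients at or above 25%, and an SD of 20 to 30 points (an assumption, as the documents give none). The mean is 25 + 0.524 × SD, that is 35.5 to 40.7 points.

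| w | True fall needed | Pass rate, SD 20 to 30 |
|---|---|---|
| 1 | 25% | 70% |
| 0.75 | 33.3% | 54% to 60% |
| 0.5 | 50% | 23% to 38% |
| 1/7 | 175% | about 0% |

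**Recruitment, for illustration.** At a 50% pass rate, 177 completers yield 177 × 0.5 = 88.5, about 88 randomised. Reaching 124 would need 124/0.5 = 248 completers and 248/0.92 = 270 enrolled, against 192 planned.

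**The case against.** The best reply is that section 8.2.6.1 only summarises the published instrument, and that visit-level scoring belongs in rater training. Section 8.2.7 requires BISS certification, section 14.1 requires third-party training on each instrument, and Appendix 2 lists the form without its text. So an instruction may exist elsewhere. That much stands. But the protocol's only stated rule is seven days, and a certified rater has no licence in it to depart from that.

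Several stronger readings are tempting, and the documents do not support them.

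- *The planned 70% response cannot be obtained.* This follows only from equal-day or worst-day scoring, and the documents specify neither. A rater who favours the current state gives a reduced rate, not zero. Section 13.8.2 also already provides for enrolling more subjects if response falls short.
- *Entry no longer depends on ketamine response.* The C-SSRS half of the gate uses since-last-visit recall and is unaffected.
- *The comparison between arms is biased.* The gate comes before randomisation, applies equally to all three arms, and randomisation is blocked by site (sections 8.1.6, 9.3 and 13.2).
- *The window contaminates relapse ratings throughout Stage 2.* The Day 10 and Day 14 windows overlap the previous visit but hold no pre-infusion time. A subject who had reached 20 at that visit would already meet the relapse definition (section 8.2.5.1.1) and be withdrawn (section 8.1). Only a Day 7 visit held on Day 6 reaches back before the infusion, by about one day in seven, and it does so in every arm.

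**Conclusion.** The point holds as a contradiction between the stated recall and the use made of the scale. Read literally, the rule mis-measures a necessary condition for randomisation: 85.7% of the rated period at 24 hours precedes the infusion (82% to 89% over 18 to 30 hours). That part is certain from the documents. The effect on the pass rate is not. It runs from none, if every rater scores current state, to a gate that cannot be met, under equal-day or worst-day scoring, and the intermediate values rest on the assumed weights and SDs. The harm is to the definition of the enriched population, to the recruitment forecast and to the Stage 2 baseline. The 25% threshold is a clinical rule and is not judged here.

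**What to change.** In section 8.2.6.1, the eCRF and rater training:

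1. Set one matched short recall for the MADRS items, for example the past 24 hours, at the dosing-day rating and at the 24-hour rating. State that the dosing-day rating is made before the infusion, and compute the percentage change between these two ratings.
2. Rate the 4-hour BISS from the infusion onward and use it descriptively only.
3. Keep the 7-day recall at screening and at Stage 2 visits, so that the entry and relapse scores of 20 stay on the same footing. Add that no post-randomisation rating may reach back before the infusion, which matters only for a Day 7 visit held early. Do not define this by the previous visit: in Table 3 that is the Day 6 phone visit, which has no BISS.
4. Check the 70% response assumption in section 13.8.2 against the definition adopted.

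Table 3 already has the BISS on the dosing day, so no visit, rating or patient is added. The cost is a wording change, an eCRF line and a training note. There are two downsides. The reliability figures cited for the 7-day BISS may not carry over exactly to a shorter recall. Change from the 24-hour baseline to later visits would also compare a 24-hour with a 7-day rating, equally in all arms, and the analysis section should say so.
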